8.3 Subject Population(s) for Analysis

A patient will be considered an evaluable study subject evaluable for data analysis per the following criteria, a written informed consent was obtained, he/she meets the inclusion and exclusion criteria, and received the GAE or sham study procedure. All subjects with 12 month followup data will be included for analysis even if some follow up data is incomplete. Every attempt will be made to ensure that there is as little missing data as possible including reminder phone calls and follow-up phone calls, if a subject misses a visit.

9 Risk Analysis

9.1 Anticipated Risks

Previous studies of lower extremity geniculate artery embolization for arthritis related pain have reported only one complication of moderate puncture site related hematoma (1/13), however this was a small population¹². A recent study of GAE for recurrent hemarthrosis completed by one of the co-Is ([name]) included 2/13 subjects who developed transient cutaneous ischemia that resolved within three weeks without intervention⁸. Additional risks that are anticipated but occur infrequently after any arterial intervention include infection, pain, pseudoaneurysm formation, arterial dissection and distal non-target embolization resulting in ischemia or necrosis. Detailed risk analysis is below:

	Risk or Side Effect	Source of Risk or Side Effect	Possible	Less Possible	Rare Events
	Discomfort	Blood draw for lab test, ultrasound or MRI	Х		
Potential Risks Associated Study	Thrombophlebitis, bruising, bleeding, blood clot, Pre- syncope or Syncope (i.e. Fainting)	Blood draw for lab tests		Х	
Enrollment	Anxiety or Claustrophobia	MRI scan		Х	
& Study Procedures	Psychological Discomfort	Clinical Trial			Х
	Infection	Blood draw for lab tests			Х
	Allergic Reaction	MRI contrast			Х

	Gadolinium contrast adverse reaction (i.e. Nephrogenic Systemic Fibrosis or severe skin reaction from contrast agent only reported in patients with kidney	MRI Contrast injection			x
	Confidentiality breach from Medical Records	Medical Record Keeping			Х
	Groin/Anesthetic Injection/Neurologic Injury/	Pressure during arterial access	Х		
	Discomfort/Pain	after catheter removed at the leg/femoral artery site	X		
	Radiation Exposure Injury	GAE/Sham procedure			Х
	Kidney Dysfunction	Contrast injected		Х	
	Joint Infection	GAE Procedure		Х	
Risks of the GAE Procedure and Post- operative care	Adverse or Allergic Reaction	Intravenous contrast agent or medications administered as part of procedure or follow-up care		х	
	Tissue damage to Skin, Muscle, Skin or other structure in legs (Non-target Embolization)	GAE/Sham procedure			Х
	Minor Bruising or Bleeding	GAE/Sham procedure			Х
	Bleeding requiring Transfusion or surgery	GAE/Sham procedure			Х
	Synovitis related symptoms including pain, stiffness or limited joint mobility	GAE procedure	X		
	Post Embolization Syndrome, including fever, malaise, headache, and myalgia (body aches)	GAE procedure		Х	
	Internal bleeding, such as Gastrointestinal bleeding	Medications taken after the procedure (i.e. Ibuprofen)			Х
	Infection	Catheter site in the leg/groin			Х
	Arterial injury/trauma, laceration, bruising/pseudoaneury	Procedure/ Closure device (clip) on the			Х
	Pulmonary embolism (clot in lung), Thrombophlebitis (clot in artery or vein)	GAE/Sham procedure and immobility			Х

Myocardial Infarction (Heart attack)	GAE/Sham procedure including moderate sedation/sedative	X
Stroke	GAE/Sham procedure including moderate sedation/sedative	X
Disability	GAE/Sham procedure including moderate sedation/sedative	X
Death	GAE/Sham procedure including moderate sedation/sedative	X

9.2 Risk Minimization

The GAE procedure will be performed by board-certified interventional radiologists who have expertise in endovascular techniques, particularly in selective catheterization and transcatheter embolization techniques. Analgesia during the procedures will be provided through the use of conscious sedation if required. The risks of conscious sedation will be minimized by continuous monitoring of heart rate, blood pressure, oxygen saturation, and cardiac rhythm. The dose area product projected for the procedure is thought to be less than 30 gray/cm2 which is about 2-4 years of background radiation and significantly less than that of a cardiac catheterization. Radiation exposure will be minimized to subjects under the principal of 'as low as reasonably achievable' (ALARA).

Sterile instruments with a sterile technique will be used to minimize infection risk at the arterial access site. Pre-operative antibiotic(s) will be administered to reduce risk of other infections, such as urinary tract. The arterial access site discomfort will be minimized by administration of local anesthesia into the overlying skin and adjacent tissues. Catheter access into the appropriate artery may be performed using ultrasound-guided arterial puncture to prevent inadvertent vessel puncture with subsequent bleeding. Real-time fluoroscopic monitoring of all catheter/wire manipulations will be used to prevent vascular injury.

The subject will be monitored for the risk of an allergic response to iodinated contrast. To minimize the risk of renal dysfunction there will be use of non-ionic contrast agents, and appropriate pre-procedure hydration, when necessary. Subjects who report an allergic reaction to iodinated contrast will be pre-medicated as per routine allergy prophylaxis per standard of care.

9.3 Adverse Event Definitions

Adverse effect. Any untoward medical occurrence in a clinical study of an investigational device; regardless of the causal relationship of the problem with the device or, if applicable, other study treatment or diagnostic product(s).

Associated with the investigational device or, if applicable, other study treatment or diagnostic product(s). There is a reasonable possibility that the adverse effect may have been caused by the investigational device or, if applicable, the other study treatment or diagnostic product(s).

*Disability*. A substantial disruption of a person's ability to conduct normal life functions.

Life-threatening adverse effect. Any adverse effect that places the subject, in the view of the investigator-sponsor, at immediate risk of death from the effect as it occurred (i.e., does not include an adverse effect that, had it actually occurred in a more severe form, might have caused death).

Serious adverse effect. Any adverse effect that results in any of the following outcomes: death, a life-threatening adverse effect, inpatient hospitalization or prolongation of existing hospitalization, a persistent or significant disability/incapacity, or a congenital anomaly/birth defect.

• *Hospitalization* shall include any initial admission (even if less than 24 hours) to a healthcare facility as a result of a precipitating clinical adverse effect; to include transfer within the hospital to an intensive care unit. Hospitalization or prolongation of hospitalization in the absence of a precipitating, clinical adverse effect (e.g., for a preexisting condition not associated with a new adverse effect or with a worsening of the preexisting condition; admission for a protocol-specified procedure) is not, in itself, a serious adverse effect.

Unexpected adverse effect. Any adverse effect, the frequency, specificity or severity of which is not consistent with the risk information described in the clinical study protocol(s) or elsewhere in the current IDE application, as amended.

Unanticipated adverse device effect. Any serious adverse effect on health or safety or any life-threatening problem or death caused by, or associated with, a device, if that effect, problem, or death was not previously identified in nature, severity, or degree of incidence in the investigational plan or IDE application (including a supplementary plan or application), or any other unanticipated serious problem associated with a device that relates to the rights, safety, or welfare of subjects.

9.4 Recording of Adverse Events

Research subjects will be questioned about adverse effects in person or by telephone the day following the procedure. In addition, they will be given a pager number to reach a physician on call, 24 hours a day, to report adverse effects and receive medical advice. The subjects will also be questioned about possible adverse effects at each follow-up visit.

All observed or volunteered adverse effects (serious or non-serious) and abnormal test findings, regardless of treatment group, if applicable, or suspected causal relationship to the investigational device or, if applicable, other study treatment or diagnostic product(s) will be recorded in the subjects' case histories. For all adverse effects, sufficient information will be pursued and/or obtained so as to permit 1) an adequate determination of the outcome of the effect (i.e., whether the effect should be classified as a *serious adverse effect*) and; 2) an assessment of the causal relationship between the adverse effect and the investigational device or, if applicable, the other study treatment or diagnostic product(s).

Adverse effects or abnormal test findings felt to be associated with the investigational device or, if applicable, other study treatment or diagnostic product(s) will be followed until the effect (or its sequelae) or the abnormal test finding resolves or stabilizes at a level acceptable to the investigator-sponsor.

An abnormal test finding will be classified as an *adverse effect* if one or more of the following criteria are met:

- The test finding is accompanied by clinical symptoms
- The test finding necessitates additional diagnostic evaluation(s) or medical/surgical intervention; including significant additional concomitant drug treatment or other therapy
 - Note: simply repeating a test finding, in the absence of any of the other listed criteria, does not constitute an adverse effect.
- The test finding leads to a change in study protocol or discontinuation of subject participation in the clinical research study
- The test finding is considered an adverse effect by the Sponsor-Investigator.

9.5 Causality and severity assessment

The investigator-sponsor will promptly review documented adverse effects and abnormal test findings to determine 1) if the abnormal test finding should be classified as an adverse effect; 2) if there is a reasonable possibility that the adverse effect was caused by the investigational device or, if applicable, other study treatment or diagnostic product(s); and 3) if the adverse effect meets the criteria for a *serious adverse effect*.

If the investigator-sponsor's final determination of causality is "unknown and of questionable relationship to the investigational device or, if applicable, other study treatment or diagnostic product(s)", the adverse effect will be classified as *associated with the use of the investigational device or study treatment or diagnostic drug product(s)* for reporting purposes. If the investigator-sponsor's final determination of causality is "unknown but not related to the investigational device or, if applicable, other study treatment or diagnostic product(s)", this determination and the rationale for the determination will be documented in the respective subject's case history.

9.6 Reporting of Adverse Effects and Unanticipated Problems

9.6.1 Reporting of adverse reactions to the FDA

The investigator-sponsor will submit a completed FDA Form 3500Ato the FDA's Center for Devices and Radiological Health for any observed or volunteered adverse effect that is determined to be an *unanticipated adverse device effect*. A copy of this completed form will be provided to all participating sub-investigators.

The completed FDA Form 3500Awill be submitted to the FDA as soon as possible and in no event, later than 10 working days after the investigator-sponsor first receives notice of the adverse effect.

If the results of the sponsor-investigator's follow-up evaluation show that an adverse effect that was initially determined to not constitute an *unanticipated adverse device effect* does, in fact, meet the requirements for reporting; the investigator-sponsor will submit a completed FDA Form 3500A as soon as possible, but in no event later than 10 working days, after the determination was made.

For each submitted FDA Form 3500A, the sponsor-investigator will identify all previously submitted reports that that addressed a similar adverse effect experience and will provide an analysis of the significance of newly reported adverse effect in light of the previous, similar report(s).

Subsequent to the initial submission of a completed FDA Form 3500A, the investigator-sponsor will submit additional information concerning the reported adverse effect as requested by the FDA.

9.6.2 Reporting Adverse Events to the Responsible IRB

In accordance with applicable policies of UNC-Chapel Hill and Vascular Institute of Virginia, the investigator will report, to the IRB, any observed or volunteered adverse effect that is determined to be (1) unexpected; (2) related or possibly related to the research; and (3) involves increased or greater risk of harm to participant(s) or others than was previously known or approved by the IRB. Adverse effect reports will be submitted to the IRB in accordance with the IRB policies and procedures.

9.7 Stopping Rules

The study will be stopped if there is greater than one major complication (Grade D, E or F) as defined by the Society of Interventional Radiology Classification System for Complications by Outcome (29).

9.8 Medical Monitoring

9.8.1 Data and Safety Monitoring Plan

Data and Safety Monitoring will be performed by a licensed physician who is not a study investigator.

Study Monitor will be:

[name], PhD UNC Department of Radiology [name]

The CRFs and any relevant source documents will be sent to the Study Monitor (as above) who will review them after treatment is complete for subjects 1, 5, 10 and 21.

Complications will be assessed by the co-PIs, categorized into major and minor categories and recorded on the CRF. CRFs and appropriate source documents will be made available to this individual for bi-monthly (every 2 months) review to ensure completeness of data collection. Any discrepancies will be immediately addressed by the co-PIs. All adverse events will be recorded and then summarized for inclusion in the final manuscript.

Data monitoring will be performed by Study Monitor listed above. CRFs and appropriate source documents will be made available to this individual for bimonthly review to ensure completeness of data collection. Any discrepancies will be immediately addressed by the co-PIs.

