3.1 General Design

This will be a single-blinded randomized-controlled study of GAE versus placebo in a small population with knee pain secondary to arthritis to determine safety and efficacy. After IRB approval of a written informed consent and over, approximately a 24 month duration, N=21 subjects will be recruited. Only subjects ≥ 40 years will be screened for study recruitment. Subjects will be randomized in a 2:1 ratio of GAE:Placebo and will be blinded from study treatment (see flow chart below). The placebo procedure will be a diagnostic angiogram of the knee, without embolization. Appropriate measures will be taken to ensure patients and nursing staff caring for the patient are blinded to assignment. Each patient will be told at the time of recruitment that they may be randomly assigned to sham, but if after 1 month they have not had symptom improvement, their assigned procedure would be revealed and, if they had undergone a sham procedure, they will be allowed to proceed with embolization. This second procedure should be shorter than a complete angiogram and embolization, as the detailed angiogram will not need to be repeated, and therefore both arms will have similar total radiation dose.

Clinical procedures and evaluations will consist of a preoperative screening assessment to determine if the potential study subject meets the inclusion and exclusion criteria, enrollment, surgical procedure for geniculate artery embolization, and follow-up visits at 24 hours, 2 weeks, 1, 3, 6, & 12 months. An MRI will be performed after the 1-month visit in those patients who underwent embolization to detect a change in synovial vascularity and to exclude complication.

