4.2 Anticipated Number of Research Subjects

Enrollment into the investigation will be defined as providing informed consent for study participation per IRB policies.

Twenty-one (21) subjects will be enrolled and all are anticipated to complete the study.

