6.5 Visit 5a and 5b - 1 Month Follow-Up

Subjects will be seen in clinic or contacted by phone or by teleconference, per the subject's preference, 30 +/- 7 days following GAE or sham procedure. The WOMAC questionnaire and VAS pain score will be completed and subjects will be evaluated for possible adverse events. An MRI of the treated knee will be acquired for those subjects who underwent GAE*. Subjects will also provide an update about the necessity/frequency of pre-established conservative therapies.

For those subjects who do not report improvement in symptoms or worsening, and are in the placebo arm, they will be unblinded and offered to undergo the geniculate artery embolization (Arm C) and then followed at similar follow-up intervals to 12 months (24 hours, 2 weeks, 1 month, 3 months, 6 months, and 12 months).

*MRI is only scheduled at one month in order to evaluate for non-target ischemic injury. These types of injuries will become apparent as early as 24 hours after embolization. Infarcted tissue will still be detectable at one month. Based on our experience with embolization in other areas, it is thought extremely unlikely that new ischemic injury related to the procedure will develop after the one-month follow-up. Additionally, findings that would be detected on later scans may be unrelated to the procedure and confound the data.

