11.1.5 Monitoring Activities

A safety monitor who is not a study investigator (see section 9.9.1) will conduct safety monitoring after treatment is complete for subjects 1, 5, 10, and 21. Adverse events will be documented and reported as described above.

The following issues will be addressed quarterly or more frequently as necessary:

- Verify receipt of all documents and supplies needed to conduct study
- Informed consent obtained for each participant
- CRF completion
- Investigational product accountability
- Check and review of the regulatory binder and all essential documents
- Clinical supply inventory
- SAE reporting
- Enrollment issues and targets
- Protocol amendment and their approval by the IRB
- Significant protocol deviations
- Personnel changes
- Updated regulatory documentation
- Any other issue as deemed important to the conduct of the study

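### Milestone safety reviews count treated subjects of both arms, not GAE procedures, so about half of GAE exposures are expected after the last milestone that could change conduct for randomised subjects

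*Combined protocol and SAP*

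**What the plan says.** **Who monitors.** Section 9.8.2 dispenses with a DSMB because the study is small and gives data and safety monitoring to one Study Monitor who is not an investigator.

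**When.** Section 9.8.1 says of the monitor: "who will review them after treatment is complete for subjects 1, 5, 10 and 21". Section 11.1.5 repeats the schedule and labels it: the monitor "will conduct safety monitoring after treatment is complete for subjects 1, 5, 10, and 21".

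**Who is counted.** Section 3.1: "Subjects will be randomized in a 2:1 ratio of GAE:Placebo". Section 4.2: "Twenty-one (21) subjects will be enrolled and all are anticipated to complete the study". The sham is an angiogram without embolization. Under Section 6.5, sham subjects without improvement at one month are unblinded and offered GAE in Arm C.

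**What is being protected.** The primary safety endpoint (Section 3.4) concerns major complications of GAE. Section 9.7 sets the stopping rule: "The study will be stopped if there is greater than one major complication (Grade D, E or F".

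**Other checks.**
- Section 9.8.1: CRFs and source documents "will be made available to this individual for bi-monthly (every 2 months) review to ensure completeness of data collection".
- Section 9.8.1, on grading: "Complications will be assessed by the co-PIs, categorized into major and minor categories and recorded on the CRF".
- Section 11.1.4: serious events are notified to the IRB, FDA *and/or* the safety monitor. The Study Monitor checks adverse events against source documents, with no time limit given.
- Section 11.1.5: SAE reporting is on a list addressed at least quarterly.
- Section 6.5, on imaging: "MRI is only scheduled at one month in order to evaluate for non-target ischemic injury".

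**The concern.** The four milestones are the only scheduled looks by an independent person that the plan labels as safety monitoring. Their trigger is a count of subjects, one in three of whom is not embolized, so a milestone does not correspond to any fixed amount of experience with the device.

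Three consequences follow. The first review may hold no GAE at all. The 11 subjects after the tenth are treated with no milestone in between, and the review at subject 21 comes after the last planned randomised procedure. Arm C procedures have no milestone of their own, and the text does not say whether treatment counts as complete before or after a crossover GAE.

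In addition, the trigger is completed treatment, so the newest subjects' one-month MRI may be missing from the review.

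At stake is whether someone outside the investigator team looks at accumulating GAE safety while conduct can still change. The limit in Section 9.7 is passed at the second major complication, so one grading decision can settle whether the trial stops, and the co-PIs make that decision.

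**Working it through.** **Inputs.** N = 21, allocated 2:1 (Sections 3.1, 4.2), read as 14 GAE and 7 sham. Milestones at treated subjects 1, 5, 10 and 21. Arm C adds 0 to 7 GAEs, so there are 14 to 21 in total. Recruitment takes about 24 months (Section 3.1). No blocking is described, so the order is taken as random.

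**Check of 14:7.** The plan gives no figure for GAEs per review, but its power figures (Section 8.1) confirm the split. Use a two-sample t-test with one-sided alpha 0.05 (taken from Section 8.2), 19 degrees of freedom and noncentrality d × √(14×7/21) = 2.160d.
- WOMAC: d = 0.16 × 12.2 / 1.9 = 1.027; power 68.95%, stated 69.1%.
- VAS: d = 0.15 × 72 / 13.3 = 0.812; power 51.85%, stated 51.7%.
- An 11:10 split would give 73.3% and 55.8%, which do not match.

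**GAEs in hand at each milestone** (hypergeometric, 14 GAE of 21)
- Subject 1: P(no GAE) = 7/21 = 33%.
- Subject 5: mean 5 × 14/21 = 3.3; P(2 or fewer) = (21 + 490 + 3185)/20349 = 18%.
- Subject 10: mean 10 × 14/21 = 6.67; 95% range 5 to 9; possible range 3 to 10.

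**Share of GAE exposures after the subject-10 review.** With g GAEs among the first ten, the share is (14 − g + crossovers after that review) / (14 + all crossovers).

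| Scenario | Share at expected g | Range for g = 9 to 5 |
|---|---|---|
| No crossover | 7.33/14 = 52% | 36% to 64% |
| All 7 cross over; sham among the first ten do so before the review | 11/21 = 52% | 52% throughout |
| All 7 cross over; even accrual over 24 months, lag 1 to 2 months | 54% to 56% (simulated mean) | – |
| The same, accrual over 12 months | 56% to 59% (simulated mean) | – |
| All 7 cross over, all after the review | 14.33/21 = 68% | 57% to 76% |

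Even accrual, the 12-month alternative and the crossover lag are assumptions. The extreme, g = 3 with all crossovers late, is 18/21 = 86%; g = 3 has probability 0.1%.

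**Other looks in the gap.** With even 24-month accrual, subjects 10 and 21 are 11 × 24/21 = 12.6 months apart, which holds about six two-monthly reviews.

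**With GAE-keyed milestones** at the 1st, 5th, 10th and, if reached, 15th GAE:
- 14 GAEs in total: 4 follow the 10th, 4/14 = 29%.
- 21 GAEs in total: 6 follow the 15th, 6/21 = 29%.
- Totals of 15 to 20 leave 0 to 5 after the 15th, at most 5/20 = 25%.

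**The case against.** **The stopping rule does not depend on these reviews.** A reader might infer that the milestones are what operates Section 9.7. The documents do not say so: the rule is a running count and can be met on any day. This stands, and it removes any claim that the rule is inoperative between milestones. It leaves open who outside the investigator team confirms that the rule has been met.

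**The gap is not unmonitored.** A reader might infer that GAEs after subject 10 have no scheduled review in time to act. That is too strong. The same monitor sees CRFs, with complication grades on them, about six times in the gap and must check adverse events against source documents. SAE reporting comes up at least quarterly. Subjects are asked about adverse effects the day after the procedure and at every visit (Section 9.4). These checks are real but weaker. The two-monthly review is for completeness of data, the source check has no timing, and *and/or* in Section 11.1.4 allows the monitor to be left out.

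**The sequence has two intermediate looks.** An empty first review is followed by reviews at subjects 5 and 10, with 3.3 and 6.7 GAEs expected. The long gap follows the third review, not the first.

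**Counting both arms is defensible.** The risk table in Section 9.1 attributes bleeding, myocardial infarction, stroke and death to GAE or sham, and Section 9.7 is not limited to one arm. This is a good reason to keep sham data in the reviews. It does not favour subject number as the trigger when the primary safety endpoint concerns GAE.

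**The MRI point is modest.** Section 6.5 says ischemic injury can appear within 24 hours, and Sections 6.3 and 7.1 allow earlier MRI when an adverse event is suspected. Arm C has its own day-1, two-week and one-month MRI visits. Only the absence of some scheduled MRI results from a given review remains.

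**Conclusion.** The point holds as a gap in independent safety oversight, partly mitigated by other checks. The milestones are not tied to GAE exposure, the first holds no GAE with probability 33%, none falls between subjects 10 and 21, and the status of Arm C is unclear.

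About half of GAE exposures, 52% to 59% in the central scenarios, are expected after the last milestone that could change conduct for randomised subjects. The subject-21 review could still inform late Arm C procedures. A reader might take two-thirds as the general figure or as a ceiling. It is neither: 68% requires every sham subject to cross over after the subject-10 review, and the conceivable extreme is 86%.

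These figures rest on 14:7 in random order. The crossover figures also rest on assumed accrual and lag. The absence of mandatory, prompt notice to the monitor rests on the wording alone. Nothing here suggests that the stopping threshold is wrong.

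**What to change.** 1. In Sections 9.8.1 and 11.1.5, trigger the milestone reviews by cumulative GAE procedures, stating that Arm C counts: for example after the 1st, 5th and 10th GAE, after the 15th if reached, and a final review. The 15th must be conditional, because without crossover only 14 GAEs take place. Keep sham data in each review.
2. State that each review includes the one-month MRI results available by then.
3. In Section 11.1.4, replace *and/or* with *and*. Add that every suspected major complication goes to the Study Monitor when it occurs, with the co-PIs' grade for independent confirmation. The added sentence is needed because that section speaks of unanticipated problems and SAEs, while Section 9.7 counts graded major complications.
4. Leave the threshold in Section 9.7 unchanged.

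**Cost.** Wording in three sections and the same monitor. There are four reviews if fewer than 15 GAEs take place, and five otherwise, one more than now. The monitor must know the running number of embolizations. The subject and the post-operative staff can remain blinded.
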